10.5.2 BEST CORRECTED DISTANCE VISUAL ACUITY (BCDVA)

BCDVA data collected at the subject Baseline, and the Week 1, 1, 3, 6, and 12 month postoperative visits. The number and percent of eyes reporting with BCDVA of 20/20 or better, 20/25 or better, 20/32 or better, 20/40 or better, worse than 20/40 to 20/80 worse than 20/80 to 20/200, and worse than 20/200 at each visit will be summarized. Also, shift tables from baseline will be presented with counts, percentages, and 95% confidence intervals.

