6.2 SAFETY ENDPOINTS

- Rates of ocular adverse events (AE) (intraoperative, postoperative)
- Reduction in best corrected distance visual acuity (BCDVA) from screening
- Secondary Ocular Surgical Interventions, including laser, for IOP control

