8.4 STUDY VISITS

8.4.1 SCREENING VISIT

Informed Consent and Point of Enrollment

Informed consent will be obtained in writing from all subjects and the process documented prior to the performance of any procedure specific to the study using the Ethics Committee approved informed consent form. The Investigator or a trained authorized designee will conduct the informed consent process. Subjects will be given ample time to read and understand the informed consent form and to consider participation in the study. Subjects will be given a copy of the signed and dated informed consent form.

After obtaining an understanding of the purpose of this study, then providing written informed consent, all potential subjects will undergo an initial screening examination in order to determine their eligibility for the study. Exams and tests listed in the Screening column of Table 1 should be performed. Refer to Appendix A for instructions for performing the exams.

The Investigator must retain the original, signed written informed consent document.

Eligibility and Study Entry

Below is a list of study procedures to be undertaken at Screening Visit which must take place from 45 days to 6 days before surgery. Data collected at screening are considered baseline data. Conduct ocular assessments in both eyes.

1.	[REDACTED]
	[REDACTED]
	[REDACTED]
	[REDACTED]

Following confirmation of eligibility per study inclusion and exclusion criteria, subjects will be scheduled for the Baseline visit allowing sufficient time for complete washout of ocular hypotensive medication (refer to Table 2). Ineligible subjects must be exited from the study. The reason for ineligibility must be documented for each enrolled subject.

Subjects who are currently taking IOP-lowering medications will undergo the washout procedure described below and in Table 2 before the Baseline visit.

Subject exam data collected prior to enrollment as part of routine patient care may serve as Screening data as long as it was collected within 15 days prior to the visit with the following exceptions:

- IOP and IOP-lowering medications. These data must be collected at the Screening visit.
- Visual fields: A historical visual field may be used IF conducted per the protocol method (Humphrey automated perimeter using the SITA Standard 24-2 testing algorithm or an Octopus perimeter program G1 or G1X.) AND is within 6 months of the Screening visit.

Washout of Hypotensive Medications

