10.6 INTERIM ANALYSIS

An interim analysis providing descriptive statistics for the outcomes may be completed following completion of the Month 6 follow-up visit by 80% of the randomized subjects. Endpoints listed below will be analyzed at an interim analysis. No device effectiveness will be claimed based on the interim analysis outcomes.

Effectiveness outcomes up to 6 months will be summarized descriptively:

1. Percent of eyes with a $\geq 20\%$ reduction in IOP with no increase in IOP-lowering medications compared to screening visit
2. Percent of eyes with IOP between 6 and 18 mmHg with no increase in IOP-lowering medications compared to screening visit
3. Percent of eyes with IOP between 6 and 21 mmHg with no increase in IOP-lowering medications compared to screening visit
4. Reduction in mean IOP from screening visit; and
5. Reduction in mean number of IOP-lowering medications from screening visit

Safety endpoints:

1. Rates of ocular adverse events (intraoperative, postoperative)
2. Reduction in BCDVA from screening (note: reduction in BCDVA due to worsening of PCO will not be treated as a safety event)
3. Secondary Ocular Surgical Interventions, including laser, for IOP control

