19.1 APPENDIX A - CLINICAL TRIAL PROCEDURES

19.1.1 BEST CORRECTED DISTANCE VISUAL ACUITY (BCDVA)

Use a standard Snellen eye chart at a distance of 6 or 4 meters. Ensure good natural light or illumination on the chart. It is important to ensure that the subject has the best possible chance of seeing and reading the test chart.

Explain the procedure to the subject. Tell subjects that it is not a test that they have to pass, but a test to help us know how their eyes are working. Tell them not to guess.

Ensure that any equipment that the subject touches is clean and is cleaned between subjects.

[REDACTED]

[REDACTED]

[REDACTED]

[REDACTED]

[REDACTED]

[REDACTED]

[REDACTED]

[REDACTED]

Manifest Refraction

Refraction will be performed by the Investigator or staff using standard clinical practice. Refractions will be performed prior to Goldmann tonometry and administration of anesthetic and dilating medication.

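### The BCDVA safety analysis gives no measure of how much acuity each eye lost, and its shift-table categories are not stated

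*Combined protocol and SAP*

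**What the plan says.** Section 6.2 and the synopsis list the safety endpoint as "Reduction in best corrected distance visual acuity (BCDVA) from screening". Neither gives a size of loss or a time point.

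Section 10.5.2 plans two summaries of acuity collected at baseline, Week 1 and Months 1, 3, 6 and 12:

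- Counts and percentages of eyes by level at each visit. The upper levels are "BCDVA of 20/20 or better, 20/25 or better, 20/32 or better, 20/40 or better". The lower levels are "worse than 20/40 to 20/80 worse than 20/80 to 20/200, and worse than 20/200 at each visit will be summarized".
- A within-eye comparison: "shift tables from baseline will be presented with counts, percentages, and 95% confidence intervals". The categories of these tables are not stated.

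Section 8.4.1 links the two reference points: "Data collected at screening are considered baseline data". A shift from baseline can therefore be read as a shift from screening.

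Section 19.1.1 gives the chart: "Use a standard Snellen eye chart at a distance of 6 or 4 meters". Its line set is not in the readable text.

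Section 10.6, on the optional descriptive interim analysis, lists the same endpoint but adds that "reduction in BCDVA due to worsening of PCO will not be treated as a safety event". Sections 6.2 and 10.5.2 contain no such exclusion.

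**The concern.** The endpoint is a change, and a reader of the safety results will want its size: how many eyes lost a meaningful amount of vision in each arm. Counts by level describe a group at a visit. A shift table shows movement within an eye, but only as finely as its categories allow. If those categories are the listed levels, resolution is coarse below 20/40, in eyes with the least acuity in reserve. Such eyes can be enrolled: the readable criteria set no acuity floor for the study eye, and the acuity exclusion in Section 7.2 concerns the fellow eye.

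The PCO note raises a second problem. The interim and final reports could count different events under one endpoint name. Section 5.2 states that investigators, site staff, sponsor clinical personnel and subjects all know the assignment after randomization. Leaving out losses because of an attributed cause is a step where that knowledge could influence the comparison between arms.

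**Working it through.** The plan states no figure to reproduce here, so the check is to see which losses the listed levels can show.

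**Step 1: make the levels usable as cells.** Four of the seven are cumulative: an eye at 20/20 also satisfies the 20/25, 20/32 and 20/40 levels. A shift table needs exclusive cells. The natural version has upper limits at 20/20, 20/25, 20/32, 20/40, 20/80 and 20/200, plus an open cell beyond 20/200. The plan does not state this choice; it is an assumption.

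**Step 2: size of loss.** For a change from 20/a to 20/b, the loss in logMAR is log10(b/a). This does not depend on the chart.

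| Change | Calculation | Loss (logMAR) | In the shift table |
|---|---|---|---|
| 20/50 to 20/80 | log10(80/50) | 0.204 | no shift |
| 20/100 to 20/200 | log10(200/100) | 0.301 | no shift |
| 20/40 to 20/50 | log10(50/40) | 0.097 | shift, one cell down |
| 20/40 to 20/80 | log10(80/40) | 0.301 | the same cell as the row above |
| 20/80 to 20/100 | log10(100/80) | 0.097 | shift, one cell down |
| 20/80 to 20/200 | log10(200/80) | 0.398 | the same cell as the row above |

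So a loss of 0.30 can be invisible while a loss of 0.10 registers, and losses of 0.10 and 0.30 can be indistinguishable.

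**Step 3: how many possible losses are hidden.** The number of lines depends on the chart, so two were assumed: (a) steps of 0.1 logMAR from 20/10 to 20/400; (b) a conventional Snellen set of 20/10, 15, 20, 25, 30, 40, 50, 60, 70, 80, 100, 200 and 400. For starting acuities of 20/20 to 20/200:

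| Loss | Chart (a), hidden / possible | Chart (b), hidden / possible |
|---|---|---|
| Two lines | 3 / 11 (20/50 to 20/80, 20/100 to 20/160, 20/125 to 20/200) | 2 / 9 (20/50 to 20/70, 20/60 to 20/80) |
| Three lines | 1 / 11 (20/100 to 20/200) | 1 / 8 (20/50 to 20/80) |

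For starting acuities of 20/20 to 20/40, no loss of one, two or three lines stays in its cell on either chart. The open ends can also hide losses: 20/10 to 20/20 is log10(20/10) = 0.301, and 20/250 to 20/400 is log10(400/250) = 0.204. These are counts of possible transitions, not of patients.

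**Step 4: lines and logMAR are not interchangeable.** On chart (a), 20/100 to 20/200 is three lines; on chart (b) these are adjacent lines. On chart (b), the two-line loss from 20/50 to 20/70 is only log10(70/50) = 0.146. A threshold in logMAR avoids this ambiguity.

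**The case against.** The strongest reply is that a shift table from baseline is already an analysis of change within each eye. Screening data count as baseline, so it addresses the stated endpoint, and tables built line by line would show every loss. That stands. A reader might infer that the plan does not measure its own endpoint, or that losses of two or three lines never appear. The documents do not support either statement: the first ignores the shift tables, and the second holds only for certain starting acuities and only if the tables reuse the listed levels.

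The upper cut-points are also about one line apart, so calling the bands wide is fair only below 20/40 and at the open ends. This stands too. Crossing a boundary still does not show the size of a loss, as 20/40 to 20/50 and 20/40 to 20/80 demonstrate.

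Third, part of the text is unreadable between Sections 9.1 and 9.3 and in Section 19.1.1. An adverse event definition based on lines lost may be there, and sight-threatening events are already serious adverse events under Section 9.1. It therefore cannot be said that large losses would escape safety reporting. The point is confined to the acuity analysis in Section 10.5.2.

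On PCO, a reader might infer that unmasked investigators will remove these losses from the final results. Section 10.6 does not say who makes the attribution, the note concerns an optional descriptive interim, and it does not say that the eyes leave the acuity tables. What stands is the difference between Section 10.6 and Sections 6.2 and 10.5.2, with no attribution rule in the readable text and an unmasked trial.

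**Conclusion.** The concern holds in a limited form. Section 10.5.2 does not state its shift categories, and the readable text gives no measure of the size of acuity loss per eye. If the listed levels are made exclusive and reused, some losses of 0.2 to 0.3 logMAR in eyes worse than 20/40 show as no shift, and losses of quite different size share a cell, including for eyes starting at 20/40. The number of eyes losing at least 0.2 or 0.3 logMAR could not then be recovered from the planned tables.

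The logMAR values are exact and independent of the chart; the line counts rest on the two assumed charts. The share of eyes affected cannot be computed without baseline acuity. The primary effectiveness analysis is not touched. The PCO exclusion is a separate inconsistency within the same endpoint, and its effect on the arm comparison is possible but not shown.

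**What to change.** In Section 10.5.2:

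- Convert each Snellen acuity to logMAR by a stated rule and report the per-eye change from screening at each visit. The rule should use nominal chart values or a small tolerance, because 20/40 to 20/63 is log10(63/40) = 0.197 and would just miss a strict 0.2 threshold.
- Report the number and percentage of eyes losing at least 0.2 and at least 0.3 logMAR (two and three lines on a chart with 0.1-logMAR steps), at 12 months and at any postoperative visit, by arm with 95% confidence intervals. The any-visit count also covers subjects withdrawn after a secondary IOP intervention under Section 8.7, who may have no 12-month acuity.
- Keep the acuity levels as a supplement, and define mutually exclusive categories for the shift tables.

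In Sections 6.2, 10.5.2 and 10.6, use one PCO rule at interim and final: count losses of any cause and show those attributed to PCO as a flagged subset, stating who makes the attribution.

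The cost is SAP wording and one additional safety table from acuities already collected. The reported BCDVA loss may look slightly less favourable than under the present wording.

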10.5.3 OTHER SAFETY OUTCOMES

The number and percent of eyes reported with each kind of slit lamp findings, gonioscopy findings, and dilated fundus examination findings at each visit will be provided.

The descriptive statistics for the continuous variables will be derived for the visual field mean deviation (MD) and pattern standard deviation (PSD).

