7 STUDY SELECTION CRITERIA

7.1 INCLUSION CRITERIA

For inclusion in this study, subjects must meet all the following criteria (only one eye of each subject is eligible, and all ocular criteria apply to the study eye only unless otherwise indicated):

1. Male or female subjects, 18 years or older
2. Pseudophakic. History of uncomplicated cataract surgery and posterior chamber IOL implantation without compromise to the lens capsule, zonular dehiscence/rupture or vitreous prolapse, [REDACTED].
3. Diagnosis of open angle glaucoma (POAG) including pigmentary and pseudoexfoliation substantiated using funduscopic exam (or OCT) and at least one reliable visual field test with the Humphrey automated perimeter using the SITA Standard 24-2 testing algorithm or an Octopus perimeter program G1 or G1X. Mean deviation score must be ≥ -12.0 dB (Humphrey) or ≤ 12.0 dB (Octopus). The visual field test may be historical (within 6 months prior to Screening Visit). If needed, visual field testing may be repeated between the Screening Visit and the Baseline Visit.
4. At the Screening visit, on 1-5 ocular hypotensive medications (fixed combinations counted as number of components) with a medicated IOP of ≤ 33 mmHg.
5. At the Baseline visit, unmedicated DIOP of ≥ 22 mmHg (≥ 24 mmHg for at least one timepoint and no less than 21 mmHg at any time point) and ≤ 36 mmHg and ≥ 3 mmHg higher than the medicated IOP at the Screening visit.
6. Scheduled for ab-interno minimally invasive canal-based glaucoma surgery.
7. Shaffer grade of ≥ 3 in all four quadrants
8. Able and willing to comply with the protocol, including all follow-up visits.
9. Understands and signs the informed consent.

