10.4.4 OTHER EFFECTIVENESS ENDPOINTS

The statistical analyses for the other effectiveness endpoints will be based on the available data of the AT population. The percent change in unmedicated DIOP from baseline at 12 months will be calculated for each study eye as

$$\% \text{ change} = \frac{(12\text{-month unmedicated DIOP} - \text{Baseline unmedicated DIOP})}{(\text{Baseline unmedicated DIOP})} \times 100\%.$$

The number and percent of subjects achieving $\geq 20\%$ reduction in unmedicated DIOP from baseline at 12 months (i.e., 12-month responder) will be calculated. The exact 95% confidence interval of the 12-month responder rate will be calculated by the binomial distribution for each study group separately. The difference in the 12-month responder between OMNI (canaloplasty AND trabeculotomy) and iStent inject groups and the corresponding 95% confidence interval per normal distribution will be calculated. The same statistics will be provided for the difference in the 12-month responder between OMNI (canaloplasty alone) and iStent inject groups. The same statistical methods will be used to summarize the subjects with an unmedicated DIOP between 6 and 18 mmHg

inclusive at 12 months.

The descriptive statistics for the continuous variables will be used to summarize the change in number of ocular hypotensive medications used from screening to 12 months. The ANOVA with study treatment group (three groups) as the factor will be used to compare the mean difference in the change in number ocular hypotensive medications used from screening to 12 months. The mean difference between OMNI (canaloplasty AND trabeculotomy) and iStent inject groups and that between OMNI (canaloplasty alone) and iStent inject groups will be evaluated using Dunnett's test. The same methods will be used to analyze the percent change in unmedicated DIOP from baseline to 12 months.

The analyses described in this section are exploratory in nature.

[REDACTED]

[REDACTED]

[REDACTED]

10.4.5 [REDACTED]

[REDACTED]

[REDACTED]

[REDACTED]

[REDACTED]

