19.1.6 DILATED FUNDUS EXAM

A mydriatic should be used to dilate the pupil so that an examination of the fundus can be conducted with an indirect ophthalmoscope and slit lamp biomicroscopy (with contact lens, Hruby lens or 60-, 66-, 78-, or 90 diopter lens). The appearance of the optic disc, macula, vessels and periphery should be evaluated and reported on the Baseline form. A measurement of the cup to disc ratio should be made and reported.

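### Section 10.5.3 counts eyes with each slit lamp, gonioscopy and fundus finding visit by visit; where a finding can be present at entry, these counts do not identify new or worse eyes if findings resolve, grades worsen or the eyes examined change.

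*Combined protocol and SAP*

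**What the plan says.** Section 10.5.3 of the combined protocol and SAP gives one summary for the three examinations: "The number and percent of eyes reported with each kind of slit lamp findings, gonioscopy findings, and dilated fundus examination findings at each visit". For the visual field it says: "The descriptive statistics for the continuous variables will be derived for the visual field mean deviation (MD) and pattern standard deviation (PSD". Section 10.5 places all safety analyses on the safety population, by arm, using whatever data are available.

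Elsewhere the plan names a within-eye comparison when it wants one. For visual acuity, section 10.5.2 adds to the per-visit categories that "shift tables from baseline will be presented with counts, percentages, and 95% confidence intervals". For medications, section 10.4.4 will "summarize the change in number of ocular hypotensive medications used from screening to 12 months".

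On disease at entry, section 7.1 requires "Diagnosis of open angle glaucoma (POAG) including pigmentary and pseudoexfoliation" and also "Shaffer grade of ≥ 3 in all four quadrants". Appendix 19.1.4 asks for any pigment dispersion at slit lamp to be noted. For the fundus, appendix 19.1.6 says: "The appearance of the optic disc, macula, vessels and periphery should be evaluated and reported on the Baseline form".

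Section 9 requires study-eye adverse events to be documented, and counts a pre-existing condition only if it becomes more severe or more frequent. Section 10.5.1 classifies events as pretreatment, intraoperative or postoperative and tabulates them by eye with 95% confidence intervals. Section 6.2 names three safety endpoints: ocular adverse events, reduction in acuity, and secondary surgical interventions for pressure. The tables in 10.5.3 are not among them.

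**The concern.** Every study eye has glaucoma at entry, and pigmentary and pseudoexfoliation forms are eligible. A postoperative count of eyes with pigment dispersion or a disc finding therefore mixes disease that was already there with anything that appeared after surgery. The safety reader wants to know how many eyes in each arm acquired a finding or got worse. The fundus reference needed for that is already recorded before surgery, but 10.5.3 does not use it.

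What is at stake is a cross-check on adverse event reporting. Under section 5.2 the investigator, site staff and subject all know the treatment after randomization, and filing an adverse event is the investigator's decision. A paired count of recorded findings would show new or worse eyes whether or not an event was filed.

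The point does not extend to findings that entry criteria already exclude. Angle width is one, since Shaffer grade 3 or more is required in all quadrants; corneal edema, named as an example in exclusion 5, is largely another. For these, a postoperative count is already close to new onset.

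**Working it through.** **Denominator.** Section 10.5.3 states no figure of its own. Section 5.1 gives 137 completers per arm and 10% dropout: 137 / 0.90 = 152.2, rounded up to 153, and 3 × 153 = 459. This reproduces the plan. The illustrations use 137 eyes examined at 12 months. All finding counts below are assumptions.

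**Is there a baseline column?** Section 10.5.2 lists Baseline first among its visits, and section 8.4.1 treats screening data as baseline data. I take it that the per-visit table in 10.5.3 would include a preoperative column.

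**Same eyes at both visits.** Let *a* eyes have the finding at baseline, *b* at 12 months, *r* be the entry findings that resolve, and *N* the eyes seen at both visits. Then

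new eyes = (b − a) + r,

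and the two counts alone bound the new eyes between max(0, b − a) and min(b, N − a).

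| a | b | N | New eyes possible | Percent of N |
|---|---|---|---|---|
| 27 | 27 | 137 | 0 to 27 | 0% to 19.7% |
| 27 | 34 | 137 | 7 to 34 | 5.1% to 24.8% |

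The lower end is the case r = 0, where every entry finding persists. The upper end needs all 27 entry findings to resolve, which is implausible for pigment or disc findings. The realistic range is near the lower end for those and wider for findings that come and go.

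**Two arms with identical tables.** Take 27 of 137 at both visits in each arm. In one arm 9 findings resolve and 9 eyes are new; in the other 2 resolve and 2 are new. The planned tables are the same. The paired table shows 9 against 2 new eyes among the 137 − 27 = 110 unaffected at entry (8.2% against 1.8%).

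**Eyes that change between visits.** Suppose 31 of 153 eyes (20.3%) have the finding at baseline, 16 eyes are not seen at 12 months, and 31 of the remaining 137 (22.6%) have it then. Between 0 and 16 of the missing eyes may have had the finding, so the baseline count among the 137 is between 15 and 31. Even with full persistence, new eyes = 31 minus that count, which is 0 to 16 (0% to 11.7% of 137). Section 8.7 gives one route to such loss: eyes needing another glaucoma procedure are withdrawn after follow-up of that procedure.

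**Worsening in grade.** An eye whose finding goes from mild to severe is counted once at each visit, so a count of eyes with the finding does not move. Section 8.4.4 refers to grading scales in 19.1.4 for the slit lamp; the scales themselves are not visible.

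**When nothing is lost.** Assume full persistence, the same 137 eyes, 20% affected at entry, and onset among unaffected eyes of 8% against 2%.

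- Level at 12 months: 0.20 + 0.80 × 0.08 = 26.4% and 0.20 + 0.80 × 0.02 = 21.6%. Difference 4.8 points; 95% half-width 1.96 × √((0.264 × 0.736 + 0.216 × 0.784)/137) = 10.1 points.
- Rise from baseline: 0.80 × 0.08 = 6.4% and 0.80 × 0.02 = 1.6%. Difference again 4.8 points; half-width 1.96 × √((0.064 × 0.936 + 0.016 × 0.984)/137) = 4.6 points.
- New findings among the 110 unaffected eyes: difference 6.0 points; half-width 1.96 × √((0.08 × 0.92 + 0.02 × 0.98)/110) = 5.7 points.

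The ratio of difference to half-width is 4.8/4.6 = 1.04 for the rise and 6.0/5.7 = 1.05 for the paired table. In this case a reader who subtracts the baseline column loses essentially nothing.

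**The case against.** The strongest reply is that the per-visit table already contains the answer. With a preoperative column beside the postoperative one, subtraction gives the new eyes exactly when entry findings persist and the same eyes are seen. Pigment and disc findings mostly do persist. This stands. A reader might compare the 10.1-point half-width of the level table with the 5.7 points of a paired table and infer a large loss of precision; that comparison ignores the baseline column and should not be used. What remains is that the planned table does not show whether persistence held or the eyes were the same.

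The second reply is that new or worse conditions are handled as adverse events under sections 9 and 10.5.1, and ocular event rates are a named endpoint. Much of this stands. Section 9.2 is not visible and may set thresholds that narrow the gap further. The slit lamp findings may also be tabulated by grade, which would show worsening in aggregate.

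A reader might also infer that 10.5.3 wrongly reports visual field MD and PSD as levels. The text says neither level nor change, and section 10.4.4 uses the same phrase about descriptive statistics for a change variable. No visible section schedules a postoperative field. Nor do the documents support a claim that MD will be pooled with mixed signs. The entry rule reads "Mean deviation score must be ≥ -12.0 dB (Humphrey) or ≤ 12.0 dB (Octopus", which shows that the sponsor knows the two perimeters differ in sign, and nothing says that they will be combined as printed.

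**Conclusion.** The point holds as a minor one. Section 10.5.3 fixes the summary of slit lamp, gonioscopy and fundus findings as counts at each visit. For findings that can be present at entry, those counts leave the number of new or worse eyes undetermined if some findings resolve, a grade worsens, or the eyes examined differ between visits. The size depends on how often that happens, which the documents do not say. With assumed counts the uncertainty runs from none, under full persistence in the same eyes, to 27 of 137 eyes in the extreme case, or 16 of 137 from loss of eyes alone.

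A reader might go further and infer a biased safety comparison. The documents do not support that: arms are randomized and tabulated at the same visits, so the same-visit difference is unbiased for the difference in prevalence among comparable eyes. What the table lacks is attribution to the individual eye. The primary analysis and the three named safety endpoints are untouched. The conclusion rests on the visible text; Table 1, section 9.2 and the slit lamp grades could reduce its practical weight but would not change what 10.5.3 specifies.

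**What to change.** Keep the tables planned in 10.5.3. Add, by arm, the number and percent of eyes with a slit lamp, fundus or gonioscopy finding (other than angle width) that is new, or worse where a grade is recorded, relative to the same eye's last preoperative examination. State as denominator the eyes examined at both times. This brings 10.5.3 into line with the acuity shift tables in 10.5.2.

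As optional wording only: where postoperative fields exist, summarize MD and PSD as within-eye change on the same perimeter type, with MD in one sign orientation.

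The cost is a few extra descriptive tables from examinations already summarized; no visit or test is added. The limits should be stated. Small counts may not settle a difference: 9 against 2 of 110 eyes gives a two-sided Fisher p of 0.059. Eyes withdrawn after re-operation are not recovered, and the examinations remain unmasked.
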